10.1 Definitions

All observed or volunteered AEs regardless of suspected causal relationship to SL-401 will be reported as described below.

10.1.1 Adverse Event (AE)

An AE is any untoward medical occurrence in a study patient who is administered a medicinal product (drug or biologic); the event may or may not have a causal relationship with the medicinal product. Examples of AEs include, but are not limited to the following:

- Clinically significant symptoms and signs including:
 - Worsening of signs and symptoms of the disease under study; disease progression without worsening of signs and symptoms as assessed by bone marrow aspiration or other methods should not be reported as AEs.
 - Signs and symptoms resulting from drug overdose, abuse, misuse, withdrawal, sensitivity, dependency, interaction, or toxicity.
 - All possibly related and unrelated illnesses, including the worsening of a preexisting illness.
 - Injury or accidents. Note that if a medical condition is known to have caused the injury or accident (hip fracture from a fall secondary to dizziness), the medical condition (dizziness) and the outcome of the accident (hip fracture from a fall) should be reported as 2 separate AEs.
- Abnormalities in physiological testing or physical examination findings that require clinical intervention or further investigation (beyond ordering a repeat confirmatory test).
- Laboratory abnormalities that meet any of the following (Note: merely repeating an abnormal test, in the absence of any of the below conditions, does not constitute an AE. Any abnormal test result that is determined to be an error does not require reporting as an AE):
 - Test result that is associated with accompanying symptoms
 - Test result that requires additional diagnostic testing or medical/surgical intervention
 - Test result that leads to significant additional concomitant drug treatment or other therapy
 - Test result that is considered to be an AE by the Investigator or Sponsor

Note that VOD, engraftment delay or failure occurring post-SCT and any changes in visual acuity and/or color vision will be followed as adverse events of special interest.

10.1.2 Serious Adverse Event (SAE)

An AE that meets one or more of the following criteria/outcomes is classified as serious:

- Results in death;
- Is life-threatening (at immediate risk of death);
- Requires admittance to the hospital or prolongation of existing hospitalization;

- Results in persistent or significant disability/incapacity;
- Results in congenital anomaly/birth disfigurements among the offspring of the patients;
- Events with medical significance or needing medical intervention to prevent the occurrence of any of the above events.

Medical judgment should be exercised in deciding whether expedited reporting is appropriate in other situations, such as important medical events that may not be immediately life-threatening or result in death or hospitalization, but may jeopardize the patient or may require intervention to prevent one of the other outcomes listed in the definition above. Serious also includes any other event that the Investigator or Sponsor judges to be serious, or which is defined as serious.

Adverse events associated with inpatient hospitalization, or prolongation of an existing hospitalization, are considered serious. Any initial admission, even if the duration is less than 24 hours is considered serious. In addition, any transfer within the hospital to an acute/intensive care unit is considered serious. However, the following hospitalizations should not be considered serious:

- Hospitalization or prolonged hospitalization in the absence of precipitating clinical AEs as follows:
 - Admission for treatment of preexisting condition not associated with the development of a new AE or with a worsening of the preexisting condition
 - Administrative admission (e.g., for a yearly physical exam)
 - Protocol-specified admission during the study (e.g., admission for SL-401 treatment)
 - Preplanned treatments or surgical procedures
 - Admission exclusively for the administration of blood products

Progression of the disease under study (including signs and symptoms of progression) should not be reported as SAEs unless the outcome is fatal during the study or within the safety reporting period. If the disease under study has a fatal outcome during the study or within the safety reporting period, then the event leading to death must be recorded as an AE and as a SAE with National Cancer Institute (NCI) Common Terminology Criteria for Adverse Events (CTCAE) Grade 5. PD is NOT an SAE; however some sequelae of disease progression (i.e., pain, thrombocytopenia) may be reported as AEs or SAEs (generally not related to investigational therapy).

The onset date of an SAE is defined as the date on which the event initially met serious criteria (e.g., the date of admission to a hospital). The end date is the date on which the event no longer met serious criteria (e.g., the date the patient was discharged from a hospital) or upon death.

10.2 Period of Observation

Clinical signs and symptoms, and AEs (regardless of relationship to study treatment) will be collected continuously from the first day of SL-401 treatment to 30 days following the last infusion of SL-401. All SAEs and AEs judged to be related to study treatment will be collected throughout the follow-up period.

Conditions that the patient experienced prior to SL-401 treatment should be recorded in the patient medical history section of the eCRF. All the AEs should be followed-up until the symptoms dissipate or become stable even if AEs continue beyond the period of observation. AEs unresolved at the end of the observation period will be considered “ongoing” with an undetermined outcome; however, if after the period of observation completes but prior to the completion of the study, additional outcome information becomes available, it will be reported. The severity of the signs, symptoms, or AEs should be determined using the NCI CTCAE, Version 4.03. A complete CTCAE list can be downloaded at <http://evs.nci.nih.gov/ftp1/CTCAE/About.html>.

All clinically meaningful abnormal test results should be retested. Abnormal test results that are difficult to associate with the study drug should be followed until normalized or until the abnormality could be clearly attributed to another cause. Abnormal test results should not be reported as AEs unless they meet the criteria outlined in [Section 10.1.1](#).

10.3 Pre-existing Conditions

A pre-existing condition will not be reported as an AE unless the condition worsens by at least one CTCAE grade during the study. The pre-existing condition, however, must be recorded in the screening eCRF as a pre-existing condition and all related concomitant medication administered for the condition recorded in the baseline (prior) concomitant medication eCRF.

10.4 Pregnancy

WOCBP and men with partners of childbearing potential must be using an adequate method of contraception to avoid pregnancy throughout the study and for up to 2 months after the study in such a manner that the risk of pregnancy is minimized. WOCBP include any female who has experienced menarche and who has not undergone successful surgical sterilization (hysterectomy, bilateral tubal ligation, or bilateral oophorectomy) or is not postmenopausal (defined as amenorrhea ≥ 12 consecutive months; or women on hormone replacement therapy with documented serum follicle-stimulating hormone level ≥ 35 mIU/mL). Even women who are using oral, implanted, or injectable contraceptive hormones or mechanical products, such as an intrauterine device or barrier methods (diaphragm, condoms, spermicides) to prevent pregnancy, are practicing abstinence, or whose partner is sterile (e.g., vasectomy), should be considered to be of childbearing potential.

WOCBP must have a negative serum or urine pregnancy test during Screening within 1 week prior to dosing. If the pregnancy test is positive, the patient must not receive study therapy and must not be enrolled in the study.

Sexually active WOCBP must use an effective method of birth control during the course of the study, in a manner such that the risk of failure is minimized.

Prior to study enrollment, WOCBP must be advised of the importance of avoiding pregnancy during study participation and the potential risk factors for an unintentional pregnancy. This information will be included in the ICF that must be signed by the patient.

In addition, all WOCBP or fertile men with partners of childbearing potential should be instructed to contact the Investigator immediately if they suspect they or their partner might be pregnant (e.g., missed or late menstrual period) at any time during study participation.

If following initiation of study treatment, it is subsequently discovered that a patient is pregnant or may have been pregnant at the time of exposure to study therapy, including during at least 2 months after product administration, study therapy will be permanently discontinued in an appropriate manner. Exceptions to discontinuation may be considered for life threatening conditions only after consultation with the Sponsor and Medical Monitor or as otherwise specified in this protocol. The Investigator must immediately notify the Sponsor and Medical Monitor of this event.

Protocol-required procedures for study discontinuation and follow-up must be performed on the patient unless contraindicated by pregnancy (e.g., x-ray studies). Other appropriate pregnancy follow-up procedures should be considered if indicated. In addition, the Investigator must report to the Sponsor follow-up information regarding the course of the pregnancy, including perinatal and neonatal outcome. Infants should be followed for a minimum of 8 weeks postpartum.

10.5 Documentation and Reporting of Adverse Events by Investigator

The Investigator is to report all directly observed AEs as well as those spontaneously reported by the patient using concise medical terminology. In addition, each patient will be questioned about AEs at each clinic visit following initiation of treatment. The question asked will be "Since your last clinic visit have you had any health problems?" or a similar non-leading question to assess health status.

The AE reporting period for this study begins upon initiation of SL-401 treatment and ends 30 days after the last infusion of SL-401. All AEs are to be reported on the AE eCRFs.

All AEs that occur in study patients during the AE reporting period specified in the protocol must be reported to the Sponsor or designee, whether or not the event is considered study treatment-related. In addition, any untoward event that occurs beyond the AE reporting period that the Investigator assesses as related to the investigational product should also be reported as an AE.

Each AE is to be classified by the Investigator as serious or non-serious. This classification of the gravity of the event determines the reporting procedures to be followed. If a SAE occurs, reporting will follow local and international regulations, as appropriate.

For any event that meets one of the SAE criteria, the Investigator [REDACTED] Safety **within 24 hours** of the knowledge of the occurrence. To report the SAE, the SAE form is to be completed electronically in the electronic data capture (EDC) system for the study. When

the form is completed, [REDACTED] personnel will be notified electronically and will retrieve the form. If the event meets serious criteria and it is not possible to access the internet, an email to should be sent to [REDACTED] or a call made to the [REDACTED]

[REDACTED] within 24 hours of awareness. When the EDC system becomes available, the SAE information must be entered within 24 hours of the system becoming available.

[REDACTED]

Each SAE should be followed until resolution, or until such time as the Investigator determines its cause or determines that, it has become stable.

Within 24 hours of receipt of follow-up information, the Investigator must update the SAE form electronically in the EDC system for the study and submit any supporting documentation (e.g., subject discharge summary or autopsy reports) to [REDACTED] via fax or e-mail. If it is not possible to access the EDC system, refer to the procedures outlined above for initial reporting of SAEs.

The Sponsor will report AEs, which are unexpected and reported as serious and associated with use of the study drug, to the US Food and Drug Administration (FDA) and all participating clinical sites. For events, which are fatal or life threatening, unexpected, and associated with use of the investigational product, a 7-Day Alert Report will be submitted to the FDA within 7 calendar days of receipt of the SAE information. For all other events that are serious, unexpected, and associated with the use of the investigational medicinal product, a written report will be made no more than 15 calendar days from the date the Sponsor learns of the event. Reports of delayed or failed engraftment post-SCT will be reported as 15-day safety reports.

10.6 Assessment of Causal Relationship to SL-401

In this study, the investigational medicinal product is SL-401. The relationship of an AE to the investigational product should be classified using the following guidelines:

- Related: A temporal relationship exists between the event onset and administration of SL-401. It cannot be readily explained by the patient's clinical state, intercurrent illness, or concomitant therapies. In case of cessation or reduction of the dose, the event abates or resolves and reappears upon rechallenge. This includes events that are considered possibly, probably, or definitely related to SL-401.

- Not Related: Evidence exists that the AE has an etiology other than the study drug (e.g., pre-existing condition, underlying disease, intercurrent illness, or concomitant medication). This includes events that are considered probably not or not related to SL-401. It should be emphasized that ineffective study drug treatment should not be considered as causally related in the context of AE reporting (in other words, disease progression is not considered an AE; however some sequelae of disease progression may be reported as AEs and should generally be reported as AEs not related to investigational therapy).

An Investigator who is qualified in medicine must make the determination of relationship to the investigational product for each AE. The Investigator should decide whether, in his or her medical judgment, there is a reasonable possibility that the event may have been caused by the investigational product. The following factors for study drug relationship should be referenced when making a determination of “related” or “not related.”

- The temporal sequence from study drug administration: The event should occur after the study drug is given. The length of time from study drug exposure to event should be evaluated in the clinical context of the event.
- Underlying, concomitant, intercurrent diseases: Each report should be evaluated in the context of the natural history and course of the disease being treated and any other disease the subject may have.
- Concomitant medication: The other medications the subject is taking or the treatment the subject receives should be examined to determine whether any of them might be recognized to cause the event in question.
- Known response pattern for this class of study drug: Clinical and/or preclinical data may indicate whether a particular response is likely to be a class effect.
- Exposure to physical and/or mental stresses: The exposure to stress might induce adverse changes in the recipient and provide a logical and better explanation for the event.
- The pharmacology and PK of the study drug: the known pharmacologic properties (absorption, distribution, metabolism, and excretion) of the study drug should be considered.

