7.5.5 Dose Delays/Modifications and Management Procedures for Toxicities Associated with SL-401

During the dosing period for each cycle, individual SL-401 infusions may be delayed to allow for toxicity resolution. Details are presented in [Table 4](#).

Monitor vital signs and check albumin, transaminases, and creatinine prior to preparing each dose of ELZONRIS.

Table 4: Recommended ELZONRIS Dose Modifications

Parameter	Severity Criteria	Dose Modification
Serum albumin	Serum albumin < 3.5 g/dL or reduced \geq 0.5 g/dL from value measured prior to initiation of the current cycle	See CLS Management Guidelines (Appendix E)
Body weight	Body weight increase \geq 1.5 kg over pretreatment weight on prior treatment day	See CLS Management Guidelines (Appendix E)
Aspartate aminotransferase (AST) or alanine aminotransferase (ALT)	ALT or AST increase $>$ 5 times the upper limit of normal	Withhold SL-401 until transaminase elevations are \leq 2.5 times the upper limit of normal.
Serum creatinine	Serum creatinine $>$ 1.8 mg/dL (159 micromol/L) or creatinine clearance $<$ 60 mL/minute	Withhold SL-401 until serum creatinine resolves to \leq 1.8 mg/dL (159 micromol/L) or creatinine clearance \geq 60 mL/minute.
Systolic blood pressure	Systolic blood pressure \geq 160 mmHg or \leq 80 mmHg	Withhold SL-401 until systolic blood pressure is $<$ 160 mmHg or $>$ 80 mmHg.
Heart rate	Heart rate \geq 130 bpm or \leq 40 bpm	Withhold SL-401 until heart rate is $<$ 130 bpm or $>$ 40 bpm.
Body temperature	Body temperature \geq 38°C	Withhold SL-401 until body temperature is $<$ 38°C.
Hypersensitivity reactions	Mild or moderate	Withhold SL-401 until resolution of any mild or moderate hypersensitivity reaction. Resume ELZONRIS at the same infusion rate.
	Severe or life-threatening	Discontinue SL-401 permanently.

Dose reductions should be discussed with the medical monitor on a case by case basis.

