4.4.2. Adverse Events

All AEs will be coded using the MedDRA coding system and displayed in tables and data listings using system organ class (SOC) and preferred term.

Analyses of AEs will be performed for those events that are considered treatment-emergent, where treatment-emergent is defined per protocol as any AE with onset after the first administration of tagraxofusp through 30 days after the last dose of tagraxofusp, or any event that was present at baseline but worsened in intensity or was subsequently considered drugrelated by the Investigator through 30 days after the last dose of tagraxofusp.

The number and percentage of patients with any treatment-emergent AE (TEAE), common AEs (defined as occurring in $\geq 10\%$ of the study sample), with any TEAE assessed by the Investigator as related to treatment, with TEAE occurring within 24 hours of infusion, with any TEAE with severity \geq Common Terminology Criteria for Adverse Events (CTCAE) Grade 3, with any serious adverse event (SAE), with any AE leading to discontinuation of study treatment, with any AE to dose reduction, and with any AE leading to dose interruption will be summarized by disease, line of therapy, dose and overall. In these tabulations, each patient will contribute only once (ie, the most related occurrence or the most intense occurrence) to each of the incidence rates in the descriptive analysis, regardless of the number of episodes.

Treatment-emergent AEs summarized by patient incidence rates are not tabulated by severity or relationship to study treatment; therefore, in such tabulations, a patient contributes only once to the count for a given AE SOC or preferred term. For tabulations that include classification by relationship to study treatment, AEs with missing relationship will be considered related to study drug. For tabulations that include classification by maximum severity grade, AEs with missing CTCAE severity will be included in a category for missing severity.

Incidence of TEAEs occurring within 24 hours of infusion will be summarized by SOC and preferred term.

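### Protocol Section 10.6 gives Investigators two incompatible causality tests and, read literally, leaves events that were never rechallenged in neither class

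*Protocol*

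**What the plan says.** Protocol Section 10.6 introduces its two classes with "The relationship of an AE to the investigational product should be classified using the following guidelines".

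- **Related.** The bullet asks for a temporal link and no ready alternative explanation, then adds: "In case of cessation or reduction of the dose, the event abates or resolves and reappears upon rechallenge". It closes with: "This includes events that are considered possibly, probably, or definitely related to SL-401".
- **Not Related.** The bullet opens with "Evidence exists that the AE has an etiology other than the study drug". It adds that sequelae of disease progression should generally be reported as not related.
- **Decision standard.** A qualified Investigator is then told to judge whether "there is a reasonable possibility that the event may have been caused by the investigational product". The factors listed are timing, other diseases, concomitant medication, class response pattern, physical or mental stress, and pharmacology and PK. Neither dechallenge nor rechallenge is among them.

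The label is used in several places. SAP 4.4.2 counts patients "with any TEAE assessed by the Investigator as related to treatment" and tabulates AESIs by causality. Protocol 10.5 bases expedited reports on association with the drug. For the time after the 30-day window, it says that "any untoward event that occurs beyond the AE reporting period that the Investigator assesses as related to the investigational product should also be reported".

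**The concern.** The Related bullet mixes a strict pharmacological proof (the event goes away off drug and returns on drug) with a broad category meant to hold anything from possible to definite. An Investigator who follows the bullet and one who follows the reasonable-possibility paragraph can label the same event differently, and both can cite Section 10.6.

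The disagreement falls on events for which rechallenge is impossible or will not be attempted, and these include some of the most serious. The study is open-label with no control arm, so Investigator attribution carries more weight than it would in a randomized comparison. If the strict test were applied, drug-related serious toxicity could be under-attributed in the causality tables, some expedited reports might not be triggered, and some late events might not be collected.

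**Working it through.** No arithmetic applies. The check sets the tests in 10.6 side by side and then traces where the label is used.

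**1. What the conditional opening does.** The rechallenge sentence applies where dosing was stopped or reduced. It therefore spares events during unchanged dosing. For events where dosing did stop, it asks for both abatement and reappearance.

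**2. Event types against each test, read literally.**

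| Event, with no evidence of another cause | Related bullet, rechallenge sentence | Not Related bullet | Reasonable possibility |
|---|---|---|---|
| Fatal | Not met: no abatement, no rechallenge | Not met | Can be judged |
| Irreversible, dosing stopped | Not met: does not abate | Not met | Can be judged |
| Treatment-ending, resolves | Not met: no rechallenge | Not met | Can be judged |
| Stopped, resolves, recurs on re-dosing | Met | Not met | Can be judged |

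The first three rows fit neither class under the bullets, but all can be classified under the reasonable-possibility test. That is the inconsistency.

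**3. Internal cross-check.** For severe or life-threatening hypersensitivity, Table 4 in Protocol 7.5.5 says "Discontinue SL-401 permanently". Such a reaction would not be rechallenged. Yet Protocol 7.6.1 lists anaphylaxis related to SL-401 among the reasons to stop treatment, and 10.5 provides a 7-day report for unexpected fatal or life-threatening events associated with the product. Both sections assume that events ending treatment or life can be related. The rechallenge sentence does not fit them.

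**4. Where the label has effect.**

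- *Tables:* related TEAEs and AESI causality (SAP 4.4.2). A baseline event also becomes treatment-emergent under SAP 4.4.2 if it is later considered drug-related, so TEAE status depends on the label in that case.
- *Expedited reports:* the association criterion in Protocol 10.5.
- *After Day 30:* Protocol 10.5 makes late reporting depend on the related call. Protocol 10.2 can be read as collecting all late SAEs, or only related ones. Veno-occlusive disease and engraftment delay or failure after transplant are followed by type (7.6.2, 10.1.1) and do not depend on the label.
- *Vision work-up:* Protocol 8.11 triggers an ophthalmologic consultation or examination for drug-related changes of Grade 2 or higher. Protocol 3.8 explains that vision is monitored because most affected patients on denileukin diftitox reported persistent impairment, a kind of event that would not abate.

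**5. Where the label has no effect.** All AEs through 30 days after the last infusion are reported whatever their causality (10.5). Grade 4 transaminase or CPK elevation counts as a DLT whatever its relationship (6.2.1). The SAP summaries of TEAEs within 24 hours of infusion, AE incidence by cycle, capillary leak syndrome by the FDA algorithm, and the Hy's Law plots do not select events by this label.

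**The case against.** The strongest reply is that 10.6 should be read as a whole. The bullets are guidelines, the rechallenge sentence is conditional, the next sentence admits possibly related events, and the operative instruction is a medical judgment of reasonable possibility. Protocol 6.2.1 describes SL-401-related toxicity in the same three grades and refers to 10.6. Sections 7.6.1 and 10.5 assume related events that were never rechallenged. A sensible Investigator would not treat rechallenge as mandatory.

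Much of this stands. A reader might infer that fatal or treatment-ending events can never be called Related. The documents do not support that, for the reasons just given. A reader might also infer that related toxicity is in fact under-reported. That does not follow either: an unexplained event does not default to Not Related, and SAP 4.4.2 counts missing causality as related. The missing-data rule gives only partial protection, because an event entered as not related is not missing.

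It is also tempting to size the problem by multiplying the 54% treatment-related transaminase rate in Protocol 3.7.2 by an assumed share of events with positive rechallenge. That figure is already attributed, so it cannot serve as a true rate, and the documents give no such share. The same section reports 65% (17 of 26) with any ALT or AST increase, so most were attributed to the drug.

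The reply does not remove the contradiction. That other sections assume a broader standard shows that the rechallenge sentence is out of line with them.

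**Conclusion.** The concern holds as an inconsistency in the causality standard, with a risk of under-attribution or of differing attribution between sites. The risk is confined to events that are fatal, irreversible, treatment-ending or otherwise never rechallenged, and to the uses of the label listed above.

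Its size cannot be given. The documents contain no count of such events by causality and do not show how Investigators applied 10.6. The conclusion rests on one assumption: that some Investigators would give weight to the rechallenge sentence as written. If all of them used reasonable possibility alone, the inconsistency would have had no effect on the data. The correction is worth making because it is cheap and the events at issue are serious.

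**What to change.** - **Rechallenge sentence in 10.6.** Delete it, or replace it with: *Positive dechallenge or rechallenge, where available, supports relatedness but is not required.*
- **Governing criterion.** State that reasonable possibility decides between Related and Not Related, so that unexplained events are classified by it. A default of Related whenever the drug cannot be excluded is not needed.
- **Disease progression.** Keep the existing text on sequelae of progression.
- **Data already recorded.** SAP 3.13.4 gives a cutoff and database lock of 13 March 2020. If causality has been entered, the sponsor should review fatal and treatment-ending events against the clarified standard in both directions, covering those called related as well as those called not related, and document the review in the CSR. Because 10.6 reserves the determination for the Investigator, disagreements should be raised with the Investigator or shown beside the recorded assessment.

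The cost is a small wording change and a short review. Some events may be relabelled, which could move the related-TEAE and AESI causality counts either way. No change to Table 4 or Section 7.6.1 is implied.
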